3.8 Discontinuation of Treatment

Subjects may be withdrawn from the study prior to completion of treatment for the following reasons:

- Subject withdrawal of consent
- Investigator's decision
- Death
- Poor maintenance of oral hygiene
- Lack of compliance
- Discontinues Orthodontics treatment and/or other treatments on study site(s) and adjacent teeth

When a subject is terminated from the study prior to completion of treatment, the subject will continue to be evaluated as scheduled. Attempts will be made to perform all follow-up assessments and procedures required by the protocol.

4.0 ADVERSE EVENTS

Recording and Reporting Adverse Events

An Adverse Event (AE) is defined as any untoward medical occurrence in a subject of a clinical investigation administered an investigational product and that does not necessarily have a causal relationship with this treatment. An AE can therefore be any unfavorable and unintended sign (including an abnormal laboratory finding), symptom, or disease temporally

associated with the use of an investigational product, whether or not related to use of the product.

Recording Adverse Events

All adverse events occurring after surgical procedure will be collected during the entire trial.

Each adverse event will be followed until the adverse event has resolved or stabilized.

During visits, subjects should be encouraged to report adverse events spontaneously or in response to general, non-directed questioning.

- Standard medical terminology for the AE and the associated body system
- Description of adverse event and clinical consequences
- Date and time of onset
- Date and time of resolution of the adverse event
- Whether or not the event is ongoing
- Severity of the event
- Relationship between the adverse event and the investigational agent or related procedure
- Description of any therapy administered and associated outcome (actions required)
- Outcome of the AE
- Whether or not the effect was serious and/or unanticipated

All AEs, regardless of seriousness, severity, or presumed relationship to study therapy, must be recorded using medical terminology in the source document and on the adverse event case report form.

Whenever possible, a diagnosis should be given when signs and symptoms are due to common etiology (e.g., cough, runny nose, sneezing, sore throat, and head congestion should be reported as “upper respiratory infection”).

Each adverse event should be reported separately. For example, “nausea and vomiting” should be recorded as two (2) separate events.

Grading Adverse Events

Common Terminology Criteria for Adverse Events v3.0, (on the NCI website, <http://ctep.info.nih.gov>) will be used to grade all toxicities/adverse events. Adverse events not included in the CTCAE v.3.0 should be reported with common medical terminology and graded according to definitions in the CTC Manual.

Assigning Relationship of Adverse Events to Treatment

A relationship must be assigned by the investigator to each reported adverse event, and will be documented as follows:

- *Unrelated* The event is clearly due to causes other than the study treatment.
- *Unlikely* Toxicity is doubtfully related to the study treatment. The event was most likely related to other factors such as the subject’s clinical state, concomitant drugs or other therapeutic interventions.
- *Possible* The event follows a reasonable temporal sequence from the time of study treatment administration, but could have been produced by

other factors such as the subject's clinical state, therapeutic interventions or concomitant drugs.

- *Probable* The event follows a reasonable temporal sequence from the time of study treatment, and follows a known response pattern to treatment. The toxicity cannot be reasonably explained by other factors such as the subject's clinical state, therapeutic interventions or concomitant drugs.
- *Definite* The event follows a reasonable temporal sequence from the time of study treatment administration, follows a known response pattern to the study treatment, cannot be reasonably explained by other factors such as the subject's condition, concomitant drugs or therapeutic interventions, AND either occurs immediately following administration of the study treatment, improves on stopping the treatment, or reappears on re-exposure.

Serious Adverse Events

Definition of a Serious Adverse Event

A Serious Adverse Event (SAE) is defined as any event meeting any of the following criteria:

- Is life-threatening or fatal
- Requires, or significantly prolongs, inpatient hospitalization
- Results in persistent or significant disability and/or incapacity
- Is a congenital anomaly or birth defect
- Requires medical or surgical intervention to prevent one of the outcomes listed above

SAE report to Sponsor and IRB

Investigators and other study site personnel must inform appropriate Sponsor representatives of any SAE that occurs during the course of the study within one day (i.e., immediately but no later than the end of the next business day) of when he or she becomes aware of it.

The Sponsor representative will work with the Investigator to compile all the necessary information and ensure that the appropriate Sponsor personnel receives a report by day one for all fatal and life-threatening cases and by day five for all other SAEs.

If an AE becomes a SAE, this and other relevant follow-up information must also be provided to Sponsor within one day for all fatal and life-threatening cases and by day five for all other SAEs.

The Investigator is responsible for informing the ethics committee of SAEs as per local requirements.

SUNSTAR IS RESPONSIBLE FOR INFORMING THE REGULATORY AUTHORITY OF DEVICE RELATED SAEs AS PER REQUIREMENTS.

5.0 STATISTICAL AND ANALYTICAL PLAN

Intent to Treat Population

The primary efficacy analysis and summaries will be performed on the “intent to treat” (ITT) population, defined as all subjects who successfully completed the screening to enter this trial.

Safety Population

All safety summaries and analyses will be performed on the safety population, defined to be all subjects.

Evaluable Population

All secondary efficacy analyses will be performed on an evaluable population, defined to be all subjects who received surgical treatment in accordance with the protocol.

Subjects exiting after undergoing surgery, but before month 6 due to treatment-related adverse events will be included in the evaluable population. Subjects that do not complete the assessments due to satisfaction with treatment will also be included in the evaluable population. All attempts will be made to collect complete follow-up evaluations for these subjects despite study exit. These subjects will be included in the analysis based on the assessments that are completed.

Subjects will be deemed non-evaluable if they do not meet the eligibility criteria as outlined in the protocol. Other reasons to be considered non-evaluable include protocol violations, as described below, and any actions that compromise the effectiveness of the treatment, for non-efficacy or safety related reasons.

Protocol violators consist of subjects who do not comply with the protocol in terms of treatment administration, visit timing, and/or assessment compliance. Each protocol violation will be discussed between Investigators and the Sponsor to evaluate the impact on the statistical assessment before performing the analyses.

Missing Data

It is not anticipated that many subjects will exit the study prematurely or will miss visits. The reasons for early termination, along with the timing of the early terminations will be provided.

Subjects missing a baseline evaluation will be discussed between Investigators and the Sponsor to evaluate the impact on the statistical assessment before performing the analyses

Assessment of Safety

Adverse events with an onset within 30 days of any surgical treatment will be recorded and tabulated. All adverse events will be tabulated by first occurrence of the event, maximum severity, and strongest relationship to study treatment by body system.

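### Membership of the evaluable population depends on outcome-related events after surgery, so the secondary efficacy results could be biased upward

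*Combined protocol and SAP*

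**What the plan says.** Section 5.0 separates two efficacy sets. For the first, "The primary efficacy analysis and summaries will be performed on the “intent to treat” (ITT) population", meaning everyone who passed screening. For the second, "All secondary efficacy analyses will be performed on an evaluable population, defined to be all subjects who received surgical treatment in accordance with the protocol".

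The Evaluable Population text then adds rules that depend on what happens after surgery.

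- Kept: "Subjects exiting after undergoing surgery, but before month 6 due to treatment-related adverse events will be included in the evaluable population".
- Kept, with no time limit: "Subjects that do not complete the assessments due to satisfaction with treatment will also be included in the evaluable population".
- Follow-up is still to be attempted for both groups, and "These subjects will be included in the analysis based on the assessments that are completed".
- Non-evaluable: ineligible subjects, protocol violators, and subjects with "any actions that compromise the effectiveness of the treatment, for non-efficacy or safety related reasons".
- Violators are subjects who depart from the protocol on treatment administration, visit timing or assessment compliance. No thresholds are given.
- Decision process: "Each protocol violation will be discussed between Investigators and the Sponsor to evaluate the impact on the statistical assessment before performing the analyses".

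Section 3.1 describes a case series of 15 subjects without a control group. Section 3.3.4 blinds staff other than the treating clinician to the treatment given. It does not mention masking to outcomes.

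**The concern.** The base definition is settled on the day of surgery, but the later rules are not. They depend on why a subject stopped attending, and that reason is related to how well the treatment worked. Two subjects can miss the same visits and be classified differently: the satisfied one is expressly kept, while the disappointed one can be treated as an assessment-compliance violator.

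The ground concerning actions that compromise effectiveness is open-ended, and its qualifier can be read in opposite ways. If non-efficacy means unrelated to efficacy, subjects who acted because of poor effect or harm stay in. If it means lack of efficacy, those same subjects come out.

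With 15 subjects and no comparator, one or two discretionary removals can shift a mean change visibly, and there is no control arm in which a similar selection might partly cancel.

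**Working it through.** **Step 1: apply the rules to an eligible subject operated on per protocol.**

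| What happens later | Rule in Section 5.0 |
|---|---|
| Stops because satisfied, at any time | Expressly kept |
| Exits before month 6, treatment-related adverse event | Expressly kept |
| Exits between months 6 and 12, treatment-related adverse event | No explicit rule |
| Exits for dissatisfaction or lack of effect | No explicit rule |
| Late or missed visits | Possible violator, discussed case by case |
| Action that compromises effectiveness | Non-evaluable, subject to the unclear qualifier |

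Follow-up runs to 12 months (Section 3.2.2), so the third row is a real interval. The base definition would admit the subjects in rows three and four, but the violator definition can remove them.

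**Step 2: who decides, and with what knowledge.** Every subject receives the same treatment, so blinding to treatment conceals little. An investigator rates healing at Week 1 (Section 3.6.3). Placing the discussion before the analyses does not place it before outcomes are recorded. Nothing in the documents says that the people discussing violations know the outcomes, and nothing prevents it.

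**Step 3: possible size.** The plan gives no standard deviation, dropout rate, effect size or power figure, so there is no figure of its own to reproduce. Inputs for an illustration:

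- N = 15 subjects (Section 3.1), with one value per subject.
- m = 2.78 mm mean probing-depth reduction, from the meta-analysis cited in Sections 1.0 and 2.0. It is used only to set a scale and is not a planning assumption. It is taken as the mean of the retained subjects.
- k = 1, 2 or 3 subjects removed (assumed).
- f = benefit of the removed subjects as a fraction of m (assumed).

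The mean over all 15 is [(N − k)m + k·f·m]/N, so the shift, evaluable minus all 15, is (k/N)(1 − f)m. For k = 2 and f = 0 this is (2/15) × 1 × 2.78 = 0.37 mm.

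| Benefit of removed subjects | k = 1 | k = 2 | k = 3 |
|---|---|---|---|
| None (f = 0) | +0.19 mm | +0.37 mm | +0.56 mm |
| Half (f = 0.5) | +0.09 mm | +0.19 mm | +0.28 mm |
| Same (f = 1) | 0 | 0 | 0 |
| 20% more (f = 1.2) | −0.04 mm | −0.07 mm | −0.11 mm |

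**Step 4: extreme case.** If the removed subjects were exactly the worst one, two or three of 15 normally distributed outcomes, simulation (200,000 draws) gives upward shifts of about 0.12, 0.23 and 0.33 standard deviations. For an assumed standard deviation of 1 to 2 mm, that is 0.12 to 0.25 mm, 0.23 to 0.46 mm and 0.33 to 0.66 mm.

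**The case against.** The best defence is that the base definition already covers every subject operated on per protocol, whatever their later reason for leaving, and that no sentence excludes dissatisfied subjects as such. That is correct and narrows the point. These subjects are exposed only if their missed visits are classed as violations. The definition permits that, while the satisfied group has a sentence protecting it.

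The retention rules also do not favour only good outcomes. Early exits for treatment-related adverse events, an unfavourable group, are kept too. This stands, up to month 6.

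Four stronger readings are tempting, and the documents do not support them.

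- A reader might infer that satisfied leavers are counted as successes. They are not: they contribute only the assessments they completed. Keeping them does not in itself inflate efficacy, and dropping them would be a selection too. The fault is the unequal treatment of other leavers.
- A reader might infer that "Poor maintenance of oral hygiene" in Section 3.8 removes a subject from the evaluable set. It is a ground for withdrawal. Section 3.8 says such subjects continue to be evaluated as scheduled, and the violator definition does not name hygiene.
- A reader might infer that the people deciding have seen each result. Section 3.1 gives the non-surgical assessments to a separate blinded examiner, and the documents do not say what outcome data the sponsor sees. The supportable criticism is that masking to outcomes is not stated.
- A reader might infer that the study's main result is affected. The primary analysis uses the ITT set, which these rules do not touch.

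**Conclusion.** The concern holds for the secondary efficacy analyses only. Section 5.0 makes evaluable status depend on outcome-related events after surgery, protects some leavers and not others, and states neither violation thresholds, nor outcome-masked classification, nor a population lock. This could bias the secondary results upward. It does not have to: direction and size depend on who is removed. On the stated assumptions the shift in mean probing-depth reduction runs from −0.11 mm to +0.56 mm for one to three removals. In the extreme worst-outcome case it reaches 0.66 mm at an assumed standard deviation of 2 mm. The plan expects few exits and gives no rate, so these figures are a range and not a forecast.

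The reach is also uncertain for another reason. Sections 3.2.1 and 3.5.2 label the listed efficacy measures as primary and no secondary endpoint is defined, so the plan does not say which results the evaluable set will produce.

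**What to change.** Rewrite the Evaluable Population text in Section 5.0 as follows.

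1. Define the set by facts fixed at surgery: the subject was eligible, and the graft and membrane were placed per protocol.
2. Apply one rule to all leavers. Keep them whatever their reason and whenever they leave, and analyse the assessments they completed.
3. Replace the clauses on satisfaction and on effectiveness-compromising actions with a short list of major violations, written in advance.
4. Have existing staff assign each subject's status without reference to outcome data, and lock it before the 6- and 12-month outcomes are reviewed.
5. Report ITT and evaluable results together, and list each excluded subject with the reason.

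The change is to wording and to the timing of one decision; it adds no subjects, visits or procedures. The drawback for the sponsor is that the evaluable-set figures may look less favourable.

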3.2.4 Safety Endpoints

Assessments of subject safety will include a tabulation of the incidence of adverse events.

All treatment-related adverse events that occur up to 30 days excepting surgery related AEs within 48 hours after any treatment will be recorded, and all serious adverse events throughout the study will be recorded.

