All treatment-related adverse events that occur up to 30 days excepting surgery related AEs within 48 hours after any treatment will be recorded in CRFs, and all serious adverse events throughout the study will be recorded.

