3.6.2 Baseline/Treatment (Visit 2)

Visit 2 may occur concurrently with Visit 1. If separate visits are to occur, Visit 2 must occur within 32 days of the screening examine.

- Examiner calibration (for first 2 subjects enrolled only)
- Preoperative and Intraoperative digital photographs
- Concomitant medications
- Surgical procedure
- Post-operative instructions
- Collection of any Adverse Events

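### Sections 3.2.4/3.4.6, 4.0 and 5.0 give three different rules for which adverse events are recorded and tabulated, and none is said to govern

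*Combined protocol and SAP*

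**What the plan says.** The protocol and SAP state the adverse event rule in three ways.

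- **Section 4.0, Recording Adverse Events.** On period: "All adverse events occurring after surgical procedure will be collected during the entire trial". On scope: "All AEs, regardless of seriousness, severity, or presumed relationship to study therapy, must be recorded", and the place of recording is "in the source document and on the adverse event case report form".
- **Section 3.2.4, Safety Endpoints, repeated at the end of section 3.4.6.** "All treatment-related adverse events that occur up to 30 days excepting surgery related AEs within 48 hours after any treatment will be recorded". Section 3.4.6 applies the same rule to the case report forms and, like 3.2.4, adds serious events for the whole study: "within 48 hours after any treatment will be recorded in CRFs, and all serious adverse events throughout the study will be recorded".
- **Section 5.0, Assessment of Safety.** "Adverse events with an onset within 30 days of any surgical treatment will be recorded and tabulated". The next sentence is "All adverse events will be tabulated by first occurrence of the event, maximum severity, and strongest relationship to study treatment by body system", with no window of its own.

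The synopsis and section 3.2.4 make tabulated adverse event incidence the safety endpoint, and the synopsis promises 12 months of safety follow-up. Only section 5.0 specifies the table. The day-of-surgery visit list (section 3.6.2) includes "Collection of any Adverse Events", and adverse events are also listed at every later visit to month 12.

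**The concern.** The three rules differ in period, in scope and in the 48-hour exception, and nothing ranks them. Sections 4.0 and 3.4.6 both address the case report form, so the difference cannot be explained as one rule for source documents and another for the form.

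Two things are at stake. The first is recording: a site that follows 3.2.4 and 3.4.6 may leave non-serious events off the form that section 4.0 requires there, and such events may not be recoverable later. The second is tabulation: if the analyst takes the 30-day sentence in 5.0 as a limit, events collected at the later visits are left out of the table. If the wording is not settled in advance, that choice could be made after the events are known.

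**Working it through.** There is no planned figure to reproduce, so the check sets the rules side by side and traces example events through each.

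**The rules compared**

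| | 4.0 | 3.2.4 / 3.4.6 | 5.0, 30-day sentence |
|---|---|---|---|
| Covers | recording | recording | recording and tabulation |
| Period, non-serious events | entire trial after surgery | up to 30 days | onset within 30 days of any surgical treatment |
| Relationship | any | treatment-related | any |
| Surgery-related, first 48 hours | included | excepted | included |
| Serious events | entire trial | throughout the study | no separate provision |

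**Example events traced through each rule**

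1. *Non-serious, surgery-related, 24 hours after surgery.* 4.0: on the form. 3.2.4/3.4.6: expressly excepted. 5.0: recorded and tabulated.
2. *Non-serious, unrelated, day 20.* 4.0: on the form. 3.2.4/3.4.6: not provided for. 5.0: recorded and tabulated.
3. *Non-serious, month 4.* 4.0: on the form. 3.2.4/3.4.6: not provided for. 5.0: outside the 30-day sentence; tabulated only if the next sentence is read as having no window.
4. *Serious, month 4.* 4.0 and 3.2.4/3.4.6: recorded. 5.0: same ambiguity as event 3, so the risk is to the table and not to recording.
5. *Any event two weeks after second-stage surgery.* Section 3.4.2 plans this surgery at 6 months for submerged implants. Because 5.0 refers to any surgical treatment, a second 30-day window can open, and this event falls inside it.

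Events 1 and 2 show that 5.0 is itself a recording rule that disagrees with 3.2.4/3.4.6. The contradiction is therefore three-way, and it would be wrong to treat 5.0 as only a filter on what was recorded elsewhere.

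**Time covered if the 30-day sentence is a limit** (12 months taken as 365 days)

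- One surgery: 30/365 = 8.2% of follow-up inside the window, 91.8% outside.
- With second-stage surgery: (30 + 30)/365 = 60/365 = 16.4% inside, 83.6% outside.

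These are shares of time, not of events. The documents give no adverse event rates or timing.

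**Effect on reported incidence.** Section 3.1 plans 15 subjects and section 5.0 defines the safety population as all subjects. Taking 15 as the denominator, one subject whose only event is left out changes incidence by 1/15 = 6.7 percentage points.

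**Other passages touching the 48-hour exception.** Visit 2 is the day of surgery and asks for any adverse event, which contradicts the exception directly. Appendix I tells the examiner to record moderate or severe sensitivity, bleeding and swelling as adverse events. The visit lists first call for the pain rating scale at Week 1 ± 3 days (days 7 − 3 = 4 to 7 + 3 = 10), and no passage clearly schedules the discomfort questionnaire within 48 hours. The form asks about duration, so it may capture something that began in that period. That is a possible overlap.

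**The case against.** The best defence is that the plan can be read as complete. Section 5.0's second sentence speaks of all adverse events, the synopsis and 3.2.4 promise incidence without a window, and 3.2.4 never says that only the named events are recorded. This stands in part: a reading in which everything is collected and tabulated is available. But it leaves the 30-day sentence with no stated purpose, and it cannot absorb the 48-hour exception, which is an express exclusion.

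A reader might infer that late serious events will be lost. The documents do not support that. Sections 3.2.4 and 3.4.6 record serious events throughout, section 4.0 requires them to be reported to the sponsor whenever they occur in the study, and their absence from the table depends on one reading of two ambiguous sentences. Nor is every event after day 30 outside the window, given the second-stage surgery. A reader might also take Appendix I as a flat contradiction of the 48-hour exception; without a scheduled completion inside 48 hours it is not one.

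It is also fair to say that the exception may be deliberate, to keep expected post-operative events from swamping the total, and that this is a small uncontrolled case series in which no efficacy result depends on the table. The first argues for displaying those events separately; it does not justify conflicting recording rules. The second limits the stakes, but adverse event tabulation is still the only stated safety endpoint.

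**Conclusion.** The conflict is real and rests on the text alone: three sections give rules for recording adverse events that cannot all be followed, and no passage resolves them. Confidence is high for the recording conflict, including the 48-hour exception against section 4.0 and the day-of-surgery visit list.

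The effect on the table is conditional. If the 30-day sentence in 5.0 is a limit, adverse events, serious ones included, with onset outside 30 days of the first surgery (and of second-stage surgery, for submerged implants) are missing from the only specified safety table, despite 12 months of safety follow-up. If it is not a limit, they are present. The text does not decide.

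No effect size can be given. The step of 6.7 points per affected subject assumes 15 subjects in the denominator and that the omitted event is the subject's only one; it shows how coarse the incidence is, not how many events would be lost. The point should be fixed, and does not put the efficacy analysis in doubt.

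**What to change.** - Reconcile 3.2.4, 3.4.6 and 5.0 to the rule already in section 4.0: all adverse events and serious adverse events after surgery through month 12 go on the case report form, with no 48-hour exception from recording.
- State in 5.0 that the main table covers the whole follow-up and includes serious events.
- Define surgery-related as distinct from treatment-related; the documents use both terms without separating them.
- Show surgery-related events within 48 hours, and events with onset within 30 days of any surgical treatment, as separate rows or tables, so that expected post-operative events do not dominate the total.

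The cost is wording in three sections. Visits 2 to 7 already collect adverse events, so no visit is added. The downside is longer tables and a higher reported adverse event incidence, which the separate display makes interpretable.
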